7.1. Data capture

Data capture will be performed using electronic patient reported outcome (PRO) collection tools implemented in the smartphone application.

Revision #: 1.0

Page: 18 of 20

PRO data collected from the smartphone application will be saved in dedicated log files on the smartphones for backup purposes.

7.2. Records and data retention

A copy of all records (e.g., informed consent documents, source data, safety reports, study device dispensing records, etc.) which support case report forms for this study, will be retained in the files of the responsible investigator for a minimum of five (5) years.

The Food and Drug Administration (FDA) and/or the local state health authorities may request access to all study records, including source documents, for inspection. The investigator and site staff agree to cooperate with these audits.

8. Device accountability

The devices will be provided by Theranica Bioelectronics (Netanya, ISRAEL). The device serial number will be documented when provided to the participant.

The devices will only be used in the clinical investigation and according to the study protocol.

The investigator will be responsible for providing device training to the participants according to the instructions for use. If the participant damages or loses the device, we can replace up to one device per participant, if needed. We will not request any compensation for that or hold any claims for that.

9. Informed consent processrescue

Informed consent and assent must be obtained from the parent/caregiver and participant, respectively, before any protocol-related activities are performed. Participants must be provided with a signed copy of the consent and assent forms.

10. Adverse events

Adverse event (AE) is defined as any unfavorable and unintended medical change, temporally associated with the use of the Nerivio, whether or not considered related to the use of the product. Any worsening (i.e., any clinically significant adverse change in frequency and/or intensity) of a preexisting condition which is temporally associated with the use of the device, is also an adverse experience. An adverse device effect (ADE) is an adverse event related to the use of the Nerivio device. In this study the ADE refers to side effect and complications.

A serious adverse event (SAE) is defined as an adverse event that leads to

Revision #: 1.0 Page: 19 of 20

- a) death,
- b) serious deterioration in the health of the subject, that either resulted in
 - 1) a life-threatening illness or injury, or
 - 2) a permanent impairment of a body structure or a body function, or
 - 3) in-patient or prolonged hospitalization, or
 - 4) medical or surgical intervention to prevent life-threatening illness or injury or permanent impairment to body structure or body function
- c) fetal distress, fetal death or a congenital abnormality or birth defect

A serious device related adverse effect (SADE) is an adverse event related to the use of the investigational device and that is considered by regulations and definitions as serious.

10.1. Characteristics of AEs

An investigator who is a qualified physician, will evaluate all adverse events as to:

Maximum intensity

Mild: awareness of symptom, but easily tolerated Moderate: definitely acting like something is wrong

Severe: extremely distressed or unable to do usual activities

Duration

Record the start and stop dates of the adverse experience. If less than 1 day, indicate the appropriate length of time and units

Relationship of an AE and SAE to the study device

The relationship of the adverse event to the study device is defined as:

Definitely related: There is evidence of exposure to the device. The temporal sequence of the AE onset relative to use of the device is reasonable. The AE is more likely explained by the device than by another cause. Dechallenge is positive. Rechallenge (if feasible) is positive. The AE shows a pattern consistent with previous knowledge of the device.

Probably related: There is evidence of exposure to the device. The temporal sequence of the AE onset relative to use of the device is reasonable. The AE is more likely explained by the device than by another cause. Dechallenge (if performed) is positive.

Possibly related: There is evidence of exposure to the device. The temporal sequence of the AE onset relative to use of the device is reasonable. The AE could have been due to another equally or less likely cause. Dechallenge (if performed) is positive.

Definitely not related: The subject/patient did not use the device; or temporal sequence of the AE onset relative to device use is not reasonable; or there is another obvious cause of the AE.

Revision #: 1.0

Page: 110 of 20

10.2. Reporting of AEs and SAEs

All adverse events will be recorded in appropriate adverse events case report form. The adverse events will be used for the safety assessment.

10.3. Anticipated device-related AEs

Possible adverse events associated with remote electrical neuromodulation include, but are not limited to, the following:

- Numbness of the hand/arm
- Itching
- Muscle spasms
- Redness
- Warmth sensation
- Tingling
- Pain in the arm

All anticipated devoice-related AEs, if present, are temporary and should disappear shortly after the treatment.

The following migraine symptoms are foreseeable and will not be considered as device related: headache, nausea, light sensitivity, sensitivity to noise, allodynia, abdominal pain, loss of appetite, cold or heat sensation, paleness, fatigue, dizziness, anxious mood, fever (rare), blurred vision, vision symptoms such as bright flashing dots or lights, blind spots, wavy or jagged lines (aura).

11. Patient confidentiality & data protection

The privacy of the participants and the confidentiality of all personal data will be maintained in reports and publications and will not be otherwise published in any way. The privacy will be maintained according to prevailing national data protection, privacy and secrecy laws. Each patient will be identified by a unique patient identification number.

12. Guidelines and applicable documents

- EN ISO 14155; (2011): Clinical investigation of medical devices for human patients
- EN ISO 14971; (2012): Medical devices Application of risk management to medical devices
- International Conference of Harmonization Good Clinical Practice guidelines
- FDA Guidance for Industry: Computerized Systems Used in Clinical Investigations

Revision #: 1.0

Page: 20 of 20

13. Reference

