4.1. Study objectives

The objective of this study is to evaluate the safety and efficacy of Nerivio[™] for the acute treatment of NDPH in adolescents. The goal of this study is to demonstrate headache relief without unexpected device-related adverse effects.

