5.3.4. Safety endpoints

1. The safety of Nerivio

The incidence of adverse events in general and by seriousness, severity and association to the device.

2. Treatment tolerability

The percent of subjects who fail to complete the study because of adverse events.

6. Statistical Considerations

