6.4.3. Safety analysis

Safety and tolerability will be assessed by review of all safety parameters, including adverse events. Serious adverse events, device-related SAEs, adverse events (by type and overall), device-related AE, adverse device reactions and device malfunction rates will be documented. Treatment tolerability, the number and percent of subjects who fail to complete the study and the number and percent of subjects who fail to complete the study because of adverse events will be presented. Time to withdrawal will also be assessed and presented by Kaplan-Meier curves.

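### Section 10.3 rules listed symptoms not device related in advance, although section 10.1 requires a physician to judge every adverse event, so device-related counts can only be equal or too low

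*Combined protocol and SAP*

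**What the plan says.** All references are to the combined protocol and SAP.

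- **Section 10.1** sets the general rule: "An investigator who is a qualified physician, will evaluate all adverse events as to" maximum intensity, duration and relationship to the device. Relationship has four categories, defined by exposure, timing, alternative cause and dechallenge (with rechallenge for the top category). No symptom is carved out. The lowest category, definitely not related, is available where, among other grounds, "there is another obvious cause of the AE".
- **Section 10.3** first lists anticipated device effects such as numbness, tingling and arm pain. It then gives a second list with this rule: "The following migraine symptoms are foreseeable and will not be considered as device related". That list runs from headache and nausea to dizziness, fatigue, anxious mood, abdominal pain, fever and blurred vision. The rule has no exception for timing, dechallenge or seriousness.
- **Section 10** counts clinically significant worsening of an existing condition as an adverse event when it is temporally associated with device use. It also defines an adverse device effect as an adverse event related to the device.
- **Section 5.3.4** makes relatedness part of a safety endpoint: "The incidence of adverse events in general and by seriousness, severity and association to the device". **Section 6.4.3** plans the matching outputs, among them "device-related SAEs, adverse events (by type and overall), device-related AE".

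**The concern.** Section 10.1 makes attribution a medical judgement on each event. Section 10.3 settles it beforehand for a broad set of symptoms. For a listed symptom that begins or worsens with stimulation and settles when stimulation stops, 10.1 can lead to possibly or probably related, whereas 10.3 leads to not related whatever was observed.

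This matters because attribution to the device is a reported safety result, and the study has one arm. In a controlled trial, an excess of dizziness or headache worsening on the device would show in the between-group comparison however individual events were attributed. Here there is no control rate, so the relatedness judgement is the main route by which such a signal could be assigned to the device. A rule that fixes the answer for some symptoms produces a reported zero that is not evidence of safety.

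**Working it through.** The plan states no figure that could be reproduced on this point. The check sets the passages side by side and then adds an illustration under stated assumptions.

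**Step 1: do the listed symptoms reach 10.1 at all?** Yes. 10.1 covers all adverse events, and section 10 makes device-associated worsening of an existing condition an adverse event. A worsening of headache after stimulation therefore falls under 10.1.

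**Step 2: where do the two rules give different answers for a listed symptom?**

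| Event as judged by the physician | Under 10.1 | Under 10.3 |
|---|---|---|
| Timing not reasonable, or another obvious cause | Not related | Not related |
| Reasonable timing, another cause equally or less likely, dechallenge positive if performed | Possibly related | Not related |
| Reasonable timing, device the more likely explanation, dechallenge positive if performed | Probably related (definitely, if its further criteria are met) | Not related |

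The rules agree in the first row, so 10.3 is not needed to keep background headache symptoms out of the device-related count. They differ only in the other rows, and always in the same direction.

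**Step 3: effect on the counts.** Let D be the number of participants with at least one device-related event under 10.1. Let r be the number among them whose only related event is a listed symptom. Under 10.3 the count is D − r, with r ≥ 0, so it is equal or lower and never higher. A participant who also has a related arm effect is still counted, so incidence per participant can shift less than the event count does. The same reasoning applies to device-related SAEs, because the rule does not exempt serious events.

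**Step 4: outputs affected.**
- Affected: incidence by association to the device (5.3.4); device-related AEs and SAEs and adverse device reactions (6.4.3), for listed symptoms.
- Not affected: overall AE incidence, AEs by type, and overall SAE counts.

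**Step 5: illustration.** The documents give no event rates. Assume N = 100 (the enrolment cap), 5 participants with a related arm effect, and r others as defined above. The count is 5 under 10.3 and 5 + r under 10.1. Intervals are exact (Clopper-Pearson), two-sided 95%.

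| Assumed r | 10.3 followed | 10.1 followed |
|---|---|---|
| 0 | 5/100 = 5.0% (1.6 to 11.3%) | 5/100 = 5.0% (1.6 to 11.3%) |
| 2 | 5/100 = 5.0% (1.6 to 11.3%) | 7/100 = 7.0% (2.9 to 13.9%) |
| 5 | 5/100 = 5.0% (1.6 to 11.3%) | 10/100 = 10.0% (4.9 to 17.6%) |

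With N = 50, the result is 5/50 = 10.0% (3.3 to 21.8%) under 10.3. Under 10.1 it is 7/50 = 14.0% (5.8 to 26.7%) for r = 2 and 10/50 = 20.0% (10.0 to 33.7%) for r = 5.

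For a single listed symptom, the device-related line would read 0/100 under 10.3. The exact upper limit is 1 − 0.025^(1/100) = 3.6%. That limit would look like an estimate from data, but the zero is set by the rule.

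**The case against.** The best defence is that 10.3 covers only foreseeable symptoms of the headache disorder and is a pre-specified use of 10.1's own obvious-cause category. Participants must have a constant headache to enter treatment (Synopsis), so such symptoms are expected throughout, and a fixed rule gives consistent coding. Per-event attribution in an open-label study is also imperfect. This has force: most listed symptoms probably would be judged unrelated, and *too low* here means relative to the plan's own standard in 10.1, not to a known true rate. It does not remove the conflict. The wording of 10.3 is categorical, and 10.1 already handles events with an obvious other cause, so the rule changes only the cases where the physician would have decided otherwise.

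A reader might infer more than the documents support:

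- **That adverse events are lost.** They are not. Section 10.2 records all adverse events and uses them for the safety assessment, and 6.4.3 presents them by type and overall.
- **That the study goal is met by definition.** Section 4.1 says: "The goal of this study is to demonstrate headache relief without unexpected device-related adverse effects". That goal concerns unexpected effects and the listed symptoms are declared foreseeable, so the link is indirect. The direct effect is on the relatedness breakdown.
- **That 10.3 contradicts itself on warmth.** It has "Warmth sensation" among device effects and "cold or heat sensation" among symptoms not device related. Context largely separates them: the first sits among local stimulation effects of an upper-arm device, the second among symptoms of the headache disorder.
- **That the safety set omits participants withdrawn for intolerance at the training visit.** Section 5.2 describes that visit before Phase 2, but the study has only two phases and the Synopsis opens Phase II with receipt of the device. Section 6.4.4 excludes the training treatment from efficacy only, and 6.4.3 reports all non-completers as well as those due to adverse events. This is at most a missing detail.

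**Conclusion.** The concern holds as a conflict between 10.1 and 10.3 that reaches a stated safety endpoint. If 10.3 is followed, device-related AE and SAE counts for the listed symptoms are zero by rule, and the totals that include them are equal to or lower than 10.1 would give. The direction follows from the text, taking the 10.1 assessment as the reference.

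The size is unknown. The base count of 5 and the values of r in the illustration are assumptions, and r = 0 gives no difference. The figures show how the result would move, not that a material bias is likely. The conflict should be corrected because the fix is cheap and the study has no control arm that could reveal the effect. It does not undermine the overall adverse event reporting.

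**What to change.** Reconcile 10.3 with 10.1. Keep the second list in 10.3 as a description of foreseeable symptoms of the headache disorder, and delete the statement that they are automatically not device related. State that every adverse event, serious events included, is assessed for relationship under 10.1, where another obvious cause remains a valid reason to classify it as not related. Warmth or heat events are classified by the same per-event assessment and need no separate rule.

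Optionally, add one sentence to 6.3 that stimulation at the second visit counts as part of the treatment phase for safety.

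The cost is a wording change, a few more relationship assessments by the investigator, and possibly slightly less favourable device-related counts. No endpoint, visit or sample size changes.
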